10.2 Reporting of Serious Adverse Events

Serious Adverse Events: A serious adverse event is any adverse event occurring at any dose or during any use of ONC201 that: Results in death; Is life threatening; Results in persistent or significant disability/incapacity; Results in or prolongs an existing inpatient hospitalization; Is a congenital anomaly/birth defect; Is a new cancer (that is not a condition of the study); Is associated with an overdose; Is another important medical event

Progression of the cancer under study is not considered an adverse event.

Any serious adverse event, or follow up to a serious adverse event, including death (beyond 30 days from last dose) due to any cause other than progression of the cancer under study that occurs to any subject from the time of initiation of therapy through 90 days following cessation of treatment, or the initiation of new anti-cancer therapy, whichever is earlier, whether or not related to ONC201, must be reported within 24 hours to Oncoceutics. Deaths, including those from disease progression that occur within 30 days of the last dose of ONC201 must be reported to Oncoceutics within 3 days of acknowledgment of patient status.

Additionally, any serious adverse event, considered by an investigator who is a qualified physician to be related to ONC201 that is brought to the attention of the investigator at any time outside of the time period specified in the previous paragraph also must be reported immediately to Oncoceutics.

Investigators **must** report to Oncoceutics any serious adverse event (SAE) that occurs after the initial dose of study treatment, during treatment, or within 3 days of the last dose of treatment on the Sponsor provided SAE form.

SAE reports and any other relevant safety information are to be forwarded to the [contact] and the Oncoceutics facsimile number within 24 hours of learning of its occurrence: [name]

Oncoceutics will submit all required SAE Reports and Annual Progress Reports to the FDA as required by FDA or other local regulators.

Investigators **must** report SAEs to the local IRB following local IRB reporting requirements.

All subjects with serious adverse events must be followed up for outcome.

10.3 Expected Toxicities

Updated toxicity information can be found in the Investigator's Brochure. Please refer to this document for expected toxicities and associated frequencies.

10.4 Adverse Events Characteristics

CTCAE term (AE description) and grade: The descriptions and grading scales found in the revised NCI Common Terminology Criteria for Adverse Events (CTCAE) version 4.03 will be utilized for AE reporting. All appropriate treatment areas should have access to a copy of the CTCAE version 4.03. A copy of the CTCAE version 4.03 can be downloaded from the CTEP web site http://ctep.cancer.gov/protocolDevelopment/electronic_applications/ctc.htm.

Attribution of the AE:

Definite – The AE is clearly related to the study treatment. Probable – The AE is likely related to the study treatment. Possible – The AE may be related to the study treatment. Unlikely – The AE is doubtfully related to the study treatment. Unrelated – The AE is clearly NOT related to the study treatment.

10.5 Pregnancy

All WOCBP should be instructed to contact the Investigator immediately if they suspect they might be pregnant (e.g., missed or late menstrual period) at any time during study participation.

In the event of a confirmed pregnancy in a patient participating in the study, the site Investigator must immediately notify Oncoceutics.

11 Efficacy

11.1 Response Evaluation Criteria in Solid Tumors (RECIST)

The Response Evaluation Criteria in Solid Tumors (RECIST v 1.1) criteria will be used for objective tumor response assessment. Response assessment would be performed at C3D1, C5D1 and at the end of every 3 cycles beyond cycle 5. All patients, including those removed from the study due to unacceptable toxicity, would undergo radiologic tumor assessment at the time of discontinuation (End of treatment). Patients who show disease progression at the first instance could continue to receive the treatment for up to 2 more cycles if the increase in tumor burden is up to 30%. Patients who continue treatment beyond

progression would undergo another confirmatory scan at the end of 2 more cycles, and if the progression is confirmed, they will be come off the study.

11.2 **Definitions**

Evaluable for adverse events. All patients will be evaluable for adverse events from the time of their first treatment with ONC201.

Evaluable for progression-free survival. All Arm B patients who have received at one dose of ONC201 will be considered evaluable for progress-free survival as the primary endpoint.

Evaluable for objective response. Only those patients who have measurable disease present at baseline, have received at least one cycle of therapy, and have had their disease reevaluated will be considered evaluable for response. These patients will have their response classified according to the definitions stated below. (Note: Patients who exhibit objective disease progression prior to the end of cycle 1 will also be considered evaluable.)

Evaluable Non-Target Disease Response. Patients who have lesions present at baseline that are evaluable but do not meet the definitions of measurable disease, have received at least one cycle of therapy, and have had their disease re-evaluated will be considered evaluable for non-target disease. The response assessment is based on the presence, absence, or unequivocal progression of the lesions.

11.3 Disease Parameters

Measurable disease. Measurable lesions are defined as those that can be accurately measured in at least one dimension (longest diameter to be recorded) as ≥ 20 mm by chest x-ray, as ≥ 10 mm with CT scan, or ≥ 10 mm with calipers by clinical exam. All tumor measurements must be recorded in millimeters (or decimal fractions of centimeters).

Note: Tumor lesions that are situated in a previously irradiated area might or might not be considered measurable.

Malignant lymph nodes. To be considered pathologically enlarged and measurable, a lymph node must be ≥ 15 mm in short axis when assessed by CT scan (CT scan slice thickness recommended to be no greater than 5 mm). At baseline and in follow-up, only the short axis will be measured and followed.

Non-measurable disease. All other lesions (or sites of disease), including small lesions (longest diameter <10 mm or pathological lymph nodes with \geq 10 to <15 mm short axis), are considered non-measurable disease. Bone lesions, leptomeningeal disease, ascites, pleural/pericardial effusions, lymphangitis cutis/pulmonitis, inflammatory breast disease, and abdominal masses (not followed by CT or MRI), are considered as non-measurable.

Note: Cystic lesions that meet the criteria for radiographically defined simple cysts should not be considered as malignant lesions (neither measurable nor non-measurable) since they are, by definition, simple cysts. 'Cystic lesions' thought to represent cystic metastases can be considered as measurable lesions, if they meet the definition of measurability described above. However, if noncystic lesions are present in the same patient, these are preferred for selection as target lesions.

Target lesions. All measurable lesions up to a maximum of 2 lesions per organ and 5 lesions in total, representative of all involved organs, should be identified as **target lesions** and recorded and measured at baseline. Target lesions should be selected on the basis of their size (lesions with the longest diameter), be representative of all involved organs, but in addition should be those that lend themselves to reproducible repeated measurements. It may be the case that, on occasion, the largest lesion does not lend itself to reproducible measurement in which circumstance the next largest lesion which can be measured reproducibly should be selected. A sum of the diameters (longest for non-nodal lesions, short axis for nodal lesions) for all target lesions will be calculated and reported as the baseline sum diameters. If lymph nodes are to be included in the sum, then only the short axis is added into the sum. The baseline sum diameters will be used as reference to further characterize any objective tumor regression in the measurable dimension of the disease.

Non-target lesions. All other lesions (or sites of disease) including any measurable lesions over and above the 5 target lesions should be identified as **non-target lesions** and should also be recorded at baseline. Measurements of these lesions are not required, but the presence, absence, or in rare cases unequivocal progression of each should be noted throughout follow-up.

11.4 Methods for Evaluation of Measurable Disease

All measurements should be taken and recorded in metric notation using a ruler or calipers. All baseline evaluations should be performed as closely as possible to the beginning of treatment and never more than 4 weeks before the beginning of the treatment.

The same method of assessment and the same technique should be used to characterize each identified and reported lesion at baseline and during follow-up. Imaging-based evaluation is preferred to evaluation by clinical examination unless the lesion(s) being followed cannot be imaged but are assessable by clinical exam.

CT and MRI This guideline has defined measurability of lesions on CT scan based on the assumption that CT slice thickness is 5 mm or less. If CT scans have slice thickness greater than 5 mm, the minimum size for a measurable lesion should be twice the slice thickness. MRI is also acceptable in certain situations (e.g. for body scans).

MRI has excellent contrast, spatial, and temporal resolution; however, there are many image acquisition variables involved in MRI, which greatly impact image quality, lesion conspicuity, and measurement. Furthermore, the availability of MRI is variable globally. As with CT, if an MRI is performed, the technical specifications of the scanning sequences used should be optimized for the evaluation of the type and site of disease. Furthermore, as with CT, the modality used at follow-up should be the same as was used at baseline and the lesions should be measured/assessed on the same pulse sequence. It is beyond the scope

of the RECIST guidelines to prescribe specific MRI pulse sequence parameters for all scanners, body parts, and diseases. Ideally, the same type of scanner should be used and the image acquisition protocol should be followed as closely as possible to prior scans. Body scans should be performed with breath-hold scanning techniques, if possible.

PET-CT: At present, the low dose or attenuation correction CT portion of a combined PET-CT is not always of optimal diagnostic CT quality for use with RECIST measurements. However, if the site can document that the CT performed as part of a PET-CT is of identical diagnostic quality to a diagnostic CT (with IV and oral contrast), then the CT portion of the PET-CT can be used for RECIST measurements and can be used interchangeably with conventional CT in accurately measuring cancer lesions over time. Note, however, that the PET portion of the CT introduces additional data which may bias an investigator if it is not routinely or serially performed.

11.5 Response Criteria

11.5.1 Evaluation of Target Lesions

Complete Response (CR): Disappearance of all target lesions. Any pathological lymph nodes (whether target or non-target) must have reduction in short axis to <10 mm.

Partial Response (PR): At least a 30% decrease in the sum of the diameters of target lesions, taking as reference the baseline sum diameters

Progressive Disease (PD): At least a 20% increase in the sum of the diameters of target lesions, taking as reference the smallest sum on study (this includes the baseline sum if that is the smallest on study). In addition to the relative increase of 20%, the sum must also demonstrate an absolute increase of at least 5 mm. (Note: the appearance of one or more new lesions is also considered progressions).

Stable Disease (SD): Neither sufficient shrinkage to qualify for PR nor sufficient increase to qualify for PD, taking as reference the smallest sum diameters while on study

11.5.2 Evaluation of Non-Target Lesions

Complete Response (CR): Disappearance of all non-target lesions and normalization of tumor marker level. All lymph nodes must be non-pathological in size (<10 mm short axis)

Note: If tumor markers are initially above the upper normal limit, they must normalize for a patient to be considered in complete clinical response.

Non-CR/Non-PD: Persistence of one or more non-target lesion(s) and/or maintenance of tumor marker level above the normal limits

Progressive Disease (PD): Appearance of one or more new lesions and/or *unequivocal progression* of existing non-target lesions. *Unequivocal progression* should not normally trump target lesion status. It must be representative of overall disease status change, not a single lesion increase.

Although a clear progression of "non-target" lesions only is exceptional, the opinion of the treating physician should prevail in such circumstances, and the progression status should be confirmed at a later time by the review panel (or Principal Investigator).

11.5.3 Evaluation of Best Overall Response

The best overall response is the best response recorded from the start of the treatment until disease progression/recurrence (taking as reference for progressive disease the smallest measurements recorded since the treatment started). The patient's best response assignment will depend on the achievement of both measurement and confirmation criteria.

Target	Non-Target	New Lesions	Overall	Best Overall Response when					
Lesions	Lesions		Response	Confirmation is Required*					
CR	CR	No	CR	>4 wks. Confirmation**					
CR	Non-CR/Non-PD	No	PR						
CR	Not evaluated	No	≥4 wks. Confirmation**						
PR	Non-CR/Non-PD /not evaluated	No	PR						
SD	Non-CR/Non-PD /not evaluated	No	SD	documented at least once \geq 4 wks. from baseline**					
PD	Any	Yes or No	PD						
Any	PD***	Yes or No	PD	no prior SD, PR or CR					
Any	Any	Yes	PD						
 See RECIST 1.1 manuscript for further details on what is evidence of a new lesion. ** Only for non-randomized trials with response as primary endpoint. *** In exceptional circumstances, unequivocal progression in non-target lesions may be accepted as disease progression. 									
Note : Patients with a global deterioration of health status requiring discontinuation of treatment without objective evidence of disease progression at that time should be reported as " symptomatic deterioration ." Every effort should be made to document the objective progression even after discontinuation of treatment.									

For Patients with Measurable Disease (i.e., Target Disease)

For Patients with Non-Measurable Disease (i.e., Non-Target Disease)

Non-Target Lesions	New Lesions	Overall Response					
CR	No	CR					
Non-CR/non-PD	No	Non-CR/non-PD*					
Not all evaluated	No	not evaluated					
Unequivocal PD	Yes or No	PD					
Any	Yes	PD					
* 'Non-CR/non-PD' is preferred over 'stable disease' for non-target disease since SD is							
increasingly used as an endpoint for assessment of efficacy in some trials so to assign this							
category when no lesions can be measured is not advised							

11.6 **Duration of Response**

Duration of overall response: The duration of overall response is measured from the time measurement criteria are met for CR or PR (whichever is first recorded) until the first date that recurrent or progressive disease is objectively documented (taking as reference for progressive disease the smallest measurements recorded since the treatment started).

The duration of overall CR is measured from the time measurement criteria are first met for CR until the first date that progressive disease is objectively documented.

Duration of stable disease: Stable disease is measured from the start of the treatment until the criteria for progression are met, taking as reference the smallest measurements recorded since the treatment started, including the baseline measurements.

11.7 **Progression-Free Survival**

Progression-free survival (PFS) is defined as the duration of time from start of treatment to time of progression or death, whichever occurs first. Progression-free survival (PFS) is defined as the time from registration to objective disease progression or death, whichever occurs first. PFS2 will be defined as the percentage of patients who exhibit PFS for >8 weeks (>56 days). Patients who have not progressed or died and are lost to follow up at 2 months will be replaced.

12 Statistical Considerations

12.1 **Primary Endpoint and Interim analyses**

Arm A and C will assess intratumoral drug concentrations and pharmacodynamics. Arm B will assess progression-free survival rate at two month following treatment initiation as primary endpoint. Patients with biopsiable disease may represent a biased subset of the overall target population since some sites of metastases will not be amenable to biopsy and therefore comparing these patients' outcomes to historical controls may not be appropriate. For this reason, only patients in Arm B will be evaluated for the primary endpoint of PFS2.

No interim analyses will be performed for Arm A or C. Pharmacodynamic effects will be evaluated by assessment of tissue biomarkers based on mechanism of action and preclinical tumor cell sensitivity studies. IHC analyses for biomarkers such as ATF4, CHOP, and DR5 will be summarized using descriptive statistics.

Intratumoral ONC201 concentration in patients will be summarized using descriptive statistics separately for Arm A and C. The targeted mean intratumoral drug concentration of ONC201 is 2.9 μ M, since this represents the mean IC50 of ONC201 in cancer cell panels profiled for in-vitro efficacy. The null hypothesis is set at a mean of 0.0 and the alternative hypothesis is set at a mean of 1.4 to account for an estimated standard deviation of 1.0. A sample size of 6 for each arm achieves 80% power to detect this difference of -1.4 between the null hypothesis mean and the alternative hypothesis with a significance level (alpha) of 0.05000 using a two-sided one-sample t-test. This assumes a normal distribution for this measurement, which is consistent with prior experience.

Below you will find a table with calculations of minimal effect size corresponding to differing SDs for a sample size of 6 patients at 80% power and a two-sided alpha of 0.05. Power is the probability of rejecting a false null hypothesis. It should be close to one. N is the size of the sample drawn from the population. To conserve resources, it should be small. Alpha is the probability of rejecting a true null hypothesis. It should be small. Beta is the

probability of accepting a false null hypothesis. It should be small. Mean0 is the value of the population mean under the null hypothesis. It is arbitrary. Mean1 is the value of the population mean under the alternative hypothesis that is relative to Mean0. Sigma is the standard deviation of the population that measures the variability in the population. Effect Size, |Mean0-Mean1|/Sigma, is the relative magnitude of the effect under the alternative.

Power	Ν	Alpha	Beta	Mean0	Mean1	S	Size
0.80000	6	0.05000	0.20000	0.0	1.4	1.0	1.435
0.80000	6	0.05000	0.20000	0.0	1.5	1.0	1.435
0.80000	6	0.05000	0.20000	0.0	1.6	1.1	1.435
0.80000	6	0.05000	0.20000	0.0	1.7	1.2	1.435
0.80000	6	0.05000	0.20000	0.0	1.8	1.3	1.435
0.80000	6	0.05000	0.20000	0.0	1.9	1.3	1.435
0.80000	6	0.05000	0.20000	0.0	2.0	1.4	1.435
0.80000	6	0.05000	0.20000	0.0	2.1	1.5	1.435
0.80000	6	0.05000	0.20000	0.0	2.2	1.5	1.435
0.80000	6	0.05000	0.20000	0.0	2.3	1.6	1.435
0.80000	6	0.05000	0.20000	0.0	2.4	1.7	1.435
0.80000	6	0.05000	0.20000	0.0	2.5	1.7	1.435
0.80000	6	0.05000	0.20000	0.0	2.6	1.8	1.435
0.80000	6	0.05000	0.20000	0.0	2.7	1.9	1.435
0.80000	6	0.05000	0.20000	0.0	2.8	2.0	1.435
0.80000	6	0.05000	0.20000	0.0	2.9	2.0	1.435

Arm B uses a Simon two-stage mini-max design [27] to evaluate the hypothesis that ONC201 will extend progression-free survival at 2 months beyond historical controls for this disease, as performed for buparlisib (NCT01397877). Historical controls for type II endometrial cancer show the null hypothesis to be 40% progression free survival at 2 months. To show the alternative hypothesis that >70% of patients exhibiting progression-free survival at 2 months with 90% power and an alpha= 5%, 24 evaluable patients are required for this arm. The probability for early termination under the null hypothesis is 63.3%.

An interim futility analysis will be performed for Arm B when the 10 evaluable patients in Arm B are evaluable for PFS2, as defined in section 11.7. In stage 1 of the study, if at least 5 of the first 10 evaluable patients exhibit progress-free survival for at least two months from treatment initiation (as defined in section 11.7), recruitment will be continued until a total of 24 evaluable patients have been enrolled for this arm. In stage two, if at least 14 patients demonstrated progress-free survival at 2 months ONC201 will be considered to have shown sufficient efficacy to warrant further study.

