2.4 Secondary Endpoints

- Safety profile of ONC201 will be determined by type, frequency, severity and timing and relationship of Adverse Events and lab abnormalities to ONC201.
- Duration of response and duration of stable disease will be determined by the time-period when a response is first seen or stable disease until disease progression.
- Overall response rate will be determined by RECIST version 1.1. Median PFS will be calculated as the period between the start of the treatment until disease progression.
- Study drug concentration in tumor tissues from patients taking once per week or twice per week on two consecutive days, about 24 hours after the single dose or second dose respectively.

3 Study Plan

We propose a Simon two-stage, non-randomized, open label, Phase II trial of ONC201 in women with metastatic or recurrent Type II endometrial cancer who failed at least 1 prior chemotherapy regimen. Patients with histologically confirmed Type II endometrial cancer,

including but not limited to serous, clear cell, carcinosarcoma, adenosquamous, and mixed histologies, will be eligible.

Arm A and C will enroll 6 evaluable patients each. All subjects in Arm A will have a biopsy of their tumor one day after the second dose of ONC201 on Cycle 1 Day 9. All subjects in Arm C will have a biopsy of their tumor one day after the 4th dose of ONC201 on Cycle 1 Day 10.

Arm B will enroll 10-24 evaluable patients.

ONC201 will be administered at a dose of 625 mg by mouth, once or twice each week until disease progression, unacceptable toxicity, or if the patient discontinues for any other reason.

It is anticipated that enrollment into this study will complete in 24 months.

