12.2 Analysis of Secondary/Exploratory Endpoints

All patients enrolled in the study who received at least 1 dose of ONC201 will be evaluated in the safety analysis using descriptive statistics including pre-treatment characteristics and concomitant treatment.

Adverse events and clinical labs will be graded according to NCI CTCAE Version 4.03. For labs without CTC grade definitions, results will be summarized as normal, abnormal or not done. Summary tables will present frequencies of patients experiencing at least one AE categorized by System Organ Class and Preferred Term according to MedDRA terminology. Listings will be prepared for each laboratory measure, and will be structured to permit review of the data by patient as they progress on treatment. Graphic displays and shift tables may be provided, as appropriate, to illustrate the results over time on study. ONC201 dose delays, dose modifications, drug exposure and duration of treatment will be also summarized.

Duration of response and duration of stable disease will be characterized using Kaplan-Meir estimates in the relevant subgroups.

Progression Free Survival (PFS) will be characterized using Kaplan-Meier curves. Median PFS will be calculated along with 95% confidence intervals. Patients who are lost to follow-up (who withdraw from the study prior to evidence of progression or death) will be censored.

12.3 **Reporting and Exclusions**

12.3.1 Evaluation of toxicity:

All patients will be evaluable for toxicity from the time of their first treatment with ONC201. Safety will be assessed by quantifying the toxicities and grades experienced by subjects who have received ONC201, including serious adverse events (SAEs). Other safety endpoints include laboratory safety assessments, vital signs and physical examinations.

A Bayesian method [27] will be used for toxicity monitoring based on the dose-limiting toxicity (DLT) rate. Patients in Arm A and Arm B will be monitored jointly for toxicity. Toxicities will be defined according to the Common Terminology Criteria for Adverse Events (CTCAE) version 4.03. DLT is defined as a clinically significant adverse event or abnormal laboratory value assessed as unrelated to disease progression, intercurrent illness, or concomitant medications and occurring during the first cycle on study that meets any of the following criteria:

- CTCAE grade 3 AST (SGOT) or ALT (SGPT) for > 7 days
- CTCAE grade 4 AST (SGOT) or ALT (SGPT) of any duration

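### Duration of response and of stable disease end at progression only; a patient who dies first has no event, and censoring her at death would overstate durability or leave it unchanged

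*Combined protocol and SAP*

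**What the plan says.** Section 2.4, repeated in the study summary, describes the two durations as the "time-period when a response is first seen or stable disease until disease progression". Section 11.6 gives the working definitions:

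- Duration of overall response runs "until the first date that recurrent or progressive disease is objectively documented".
- Duration of complete response runs "until the first date that progressive disease is objectively documented".
- For stable disease: "Stable disease is measured from the start of the treatment until the criteria for progression are met".

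Death appears in none of them. In 11.7, by contrast, PFS is "defined as the duration of time from start of treatment to time of progression or death, whichever occurs first".

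For the analysis, 12.2 states: "Duration of response and duration of stable disease will be characterized using Kaplan-Meir estimates in the relevant subgroups". It names a median only for PFS: "Median PFS will be calculated along with 95% confidence intervals". Its single censoring rule concerns patients lost to follow-up and belongs to the PFS paragraph. Nothing says how a patient who dies without documented progression enters the two duration analyses.

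**The concern.** A Kaplan-Meier analysis needs an end point for every patient: an event or a censoring time. With progression as the only event, a patient in response or with stable disease who dies first cannot contribute an event. The natural reading is that she is censored at death. Kaplan-Meier would then treat her as having the same prospects as patients still alive and in response, which is informative censoring.

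The plan leaves room for such deaths. Section 11.5.3 foresees patients stopping for general deterioration without objective progression. Section 3 accepts a scan from the previous 30 days in place of a new end-of-treatment scan. Section 5.4 collects later imaging only where it exists, but follows patients every 30 days until death. Deaths are therefore likely to be captured more completely than late progressions.

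At stake is how two secondary efficacy endpoints are read. A durability claim could rest partly on patients who died, and could sit awkwardly beside a PFS curve that counts the same deaths.

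**Working it through.** The documents give no median, rate or sample size for either duration, so there is no planned figure to reproduce.

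**1. Can death come before documented progression?** Scans fall on day 1 of cycles 3 and 5 (sections 3 and 11.1). With 21-day cycles these are days 2 × 21 + 1 = 43 and 4 × 21 + 1 = 85, a gap of 42 days. A patient stable on day 43 who dies before day 85 without another scan has a PFS event on the day of death. Under 11.6 her stable disease has no end.

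**2. Does another section supply the event?** Section 12.3.2 treats early death as treatment failure, but only when a response category is assigned. It gives no end date to a patient already classed as complete response, partial response or stable disease.

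**3. Direction, if censored at the date of death.** The Kaplan-Meier estimate is the product over event times of (1 − d/n), where d is the number of events and n the number at risk. Changing a death from event to censoring at the same date leaves n unchanged and lowers d. Every factor stays the same or rises, so the curve is never lower. Stable disease and PFS (in the first of the two definitions in 11.7) both start at start of treatment. For the same patients, the stable disease curve would then lie on or above the PFS curve.

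**4. Illustrative size.** Let progression have constant hazard hP, death without progression have constant hazard hD, and s = hD/(hP + hD).

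- Median with death as an event: ln 2/(hP + hD)
- Median with deaths censored at death: ln 2/hP
- Ratio: (hP + hD)/hP = 1/(1 − s)

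Neither s nor the 4.0-month median below is in the documents; both are assumed.

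| s | Ratio | Median reads (4.0 months with death as an event) |
|---|---|---|
| 0% | 1.00 | 4.0 |
| 5% | 1.05 | 4.2 |
| 10% | 1.11 | 4.4 |
| 20% | 1.25 | 5.0 |
| 30% | 1.43 | 5.7 |
| 40% | 1.67 | 6.7 |

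A simulation with 100,000 patients gave 4.45, 5.01 and 5.77 months at s = 10%, 20% and 30%, in line with the formula. In small samples the median with deaths censored was never shorter. It was longer in 41%, 67% and 83% of runs with 10 patients, and in 66%, 90% and 97% with 20. Arm B has 10 to 24 evaluable patients, so the subgroups will be small.

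**5. Does the direction depend on the censoring date?** Yes. Take progressions at months 3 and 4, and a third patient with a last scan at 1.5 who dies at 8.

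- Censored at 1.5: two at risk at month 3, survival 1/2, median 3.
- Death as an event at 8: survival 2/3 at month 3 and 1/3 at month 4, median 4.

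Counting the death lengthens the median here.

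**6. Primary endpoint.** The Arm B rule (at least 5 of 10, then at least 14 of 24; 40% against 70%) reproduces the stated early-termination probability of 63.3%, with type I error 4.8% and power 90.1%. It uses PFS, which counts death, and is unaffected.

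**The case against.** A reader might infer that the plan prescribes censoring at death and that its Kaplan-Meier medians are therefore too long. The documents do not support that. Section 12.2 promises estimates for these durations, not medians, and no censoring rule for death is written. If the analyst censored at the last scan instead, the bias could run the other way, as step 5 shows. This objection stands: the overstatement is conditional on censoring at the date of death.

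Other text makes deaths without documented progression less frequent. Sections 3 and 11.1 require imaging at discontinuation for all patients, including those stopping for toxicity. Section 11.5.3 asks sites to try to document progression after treatment stops. These provisions reduce the problem without removing it.

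The omission may be shorthand, since 2.4 also describes median PFS without mentioning death although 11.7 includes it. That is plausible for 2.4. It is weaker for 11.6, which is the detailed definition and requires objective documentation.

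Finally, both durations are secondary and descriptive, with no hypothesis or decision rule, and PFS is reported beside them. That limits the importance of the point but does not answer it.

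**Conclusion.** The point holds in conditional form. The definitions give no event to a patient who dies in response or with stable disease, and nothing elsewhere supplies one. This is a stated event rule that differs from the plan's own PFS rule, not merely a missing detail.

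The size cannot be found from the documents and its lower bound is zero. The increases of 11%, 25% and 43% rest on assumed death shares and constant hazards, and should not be read as predictions for this trial. The effect is confined to the secondary durability endpoints.

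**What to change.** - In the study summary, 2.4 and 11.6, end duration of response, of complete response and of stable disease at objective progression or death from any cause, whichever is first.
- In 12.2, censor patients alive without progression at their last adequate tumor assessment.
- Apply to these durations the same rule as PFS for deaths after missed scans or after new anti-cancer therapy. The plan states no such rule for PFS at present, so one should be written to serve both.

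The cost is wording. Deaths and new anti-cancer treatments are already followed every 30 days under 5.4, so no visits or patients are added. Reported durations may be shorter. The third item is needed because, once death is an event, a death long after the last scan would otherwise count as response or stable disease continuing up to that date.
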